1 STUDY DETAILS

1.1 Study Objectives

Primary objective:

Protocol

To evaluate if fetal valvuloplasty in aortic stenosis improves outcomes up to 2 years after birth compared with no fetal valvuloplasty, measured with transplantation-free survival from fetal diagnosis to 2 years postnatal age with a biventricular circulation without pulmonary hypertension at that time.

Secondary objective:

To evaluate fetal and maternal safety of fetal valvuloplasty.

- Intervention-related fetal death (defined as fetal death within 24 hours of procedure).
- Fetal death not directly related to the intervention, except termination of pregnancy.
- Maternal complications to procedure (requiring intensive care or resulting in maternal death).
- Preterm delivery < 37 weeks.
- Fetal left heart growth from the point of study inclusion until just before the first postnatal catheter or surgical intervention

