1.3 Inclusion and Exclusion Criteria

1.3.1 Inclusion Criteria

Inclusion criteria represent currently used criteria for fetal intervention in aortic stenosis. They are identical in the intervention and the non-intervention groups.

Protocol

Statistical Analysis Plan

Effect of fetal aortic valvuloplasty on outcomes

Protocol No:

1.0

A. All of the following echocardiographic criteria need to be satisfied between 23+0 and 31+6 weeks (z-scores* according to schneider):

- 1 Aortic valve stenosis with antegrade flow through the valve
- 2 Predominantly left-to-right shunt at the atrial level
- 3 Predominantly retrograde flow in the aortic arch between the first two brachiocephalic vessels
- 4 Qualitatively depressed left ventricular function
- 5 LV end-diastolic diameter z-score* > +/-0
- 6 Left ventricular inlet length in diastole, z-score* according to gestational age
 - a. GA ≤ 24+6: Z-score > ±0
 - b. GA 25+0 to 27+6: Z-score > -0.75
 - c. $GA \ge 28+0$: Z-score > -1.50
- 7 Mitral valve diameter in diastole z-score* > -2.0
- B. All of the following postnatal treatment options need to be available:
- 1 Surgical or catheter based aortic valvotomy
- 2 Ross-Konno surgery
- 3 Norwood or hybrid stage-one surgery

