3.4.2 Secondary Efficacy Variables

Secondary efficacy variables in this study are as following:

- Transplantation-free survival from fetal diagnosis to 2 years of age (analysed as time to event on FAS_{ENR} (main analysis), FAS_{BIRTH} (followed from birth), PP_{ENR} and PP_{BIRTH} (followed from birth), overall for FAV 1+2 vs no-FAV 1+2 (main analysis), and descriptively FAV 1 vs no-FAV 1 and FAV 1 vs no-FAV 1+2).
- Survival from fetal diagnosis to live birth (analysed as time to event on FAS_{ENR} (main analysis) and PP_{ENR}, overall for FAV 1+2 vs no-FAV 1+2 (main analysis), and descriptively FAV 1 vs no-FAV 1 and FAV 1 vs no-FAV 1+2).

Protocol

Statistical Analysis Plan

Effect of fetal aortic valvuloplasty on outcomes

- Proportion of included patients who have a biventricular circulation at neonatal hospital discharge (analysed on FAS_{ENR} (main analysis), FAS_{BIRTH}, PP_{ENR} and PP_{BIRTH}, overall for FAV 1+2 vs no-FAV 1+2 (main analysis), and descriptively FAV 1 vs no-FAV 1 and FAV 1 vs no-FAV 1+2).
- Proportion of included patients who have a biventricular circulation at 2 years of age (analysed on FAS_{ENR} (main analysis), FAS_{BIRTH}, PP_{ENR} and PP_{BIRTH}, overall for FAV 1+2 vs no-FAV 1+2 (main analysis), and descriptively FAV 1 vs no-FAV 1 and FAV 1 vs no-FAV 1+2).
- Number of postnatal catheter and/or surgical procedures before 2 years of age (analysed on FAS_{BIRTH} (main analysis) and PP_{BIRTH}, overall for FAV 1+2 vs no-FAV 1+2 (main analysis), and descriptively FAV 1 vs no-FAV 1 and FAV 1 vs no-FAV 1+2).

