3.5.2 Fetal aortic valvuloplasty - technical details

The following details about the fetal cardiac intervention are among those that will be recorded:

• Type of maternal anesthesia

STATISTISKA KONSULTGRUPPEN	Statisti	cal Analysis Plan
Protocol: Effect of fetal aortic valvuloplasty on outcomes	Protocol No):
	Version: 1.0	Page 19 of 26

- Pre- and procedural fetal medication
- Fetal resuscitation drugs used
- Size of needle
- Number of cardiac punctures
- Diameter of balloon
- Balloon to aortic valve diameter ratio
- Inflation pressure
- Number of inflations
- Technical success by criteria

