3.5.3 Fetal and maternal complications of fetal intervention

Safety of the prenatal procedure will be evaluated through the following variables:

- Intervention-related fetal death (defined as fetal death within 24 hours of procedure)
- Fetal death not directly related to the intervention, except termination of pregnancy
- Maternal complications to procedure (requiring intensive care or resulting in maternal death)
- Preterm delivery < 37 weeks
- Reasons for fetal or postnatal death

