4.7.2 Intervention and Technical Details

Information about intervention and its technical details will be summarized on safety population per treatment groups.

Complications of fetal intervention and maternal complications 4.7.3

Data regarding complications and reasons for death will be described for safety population per treatment groups. No formal tests will be performed.

STATISTISKA KONSULTGRUPPEN	Statisti	cal Analysis Plan
Protocol: Effect of fetal aortic valvuloplasty on outcomes	Protocol No):
	Version: 1.0	Page 25 of 26

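### Both death rows in the safety objective count fetal deaths only, so a newborn who dies after delivery within 24 hours of a fetal procedure is in no procedure-linked count

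*SAP*

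**What the plan says.** The safety objective has two mortality rows, worded alike in the Protocol (Secondary objective) and in SAP 1.1 and 3.5.3. The first is "Intervention-related fetal death (defined as fetal death within 24 hours of procedure"). The second is "Fetal death not directly related to the intervention, except termination of pregnancy". A third row, "Preterm delivery < 37 weeks", records the timing of delivery and not what happens to the child.

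SAP 3.5.3 adds one item that reaches past birth: "Reasons for fetal or postnatal death". It has no time window, no rule linking a postnatal death to the procedure, and no rate. For the analysis, SAP 4.7.3 says: "Data regarding complications and reasons for death will be described for safety population per treatment groups". No formal tests are planned. The output is Table 3.2.1.

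On timing, SAP 1.3.1 states: "All of the following echocardiographic criteria need to be satisfied between 23+0 and 31+6 weeks". The Protocol's eCRF section makes the baseline echo the last examination before any intervention.

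The secondary efficacy list in SAP 3.4.2 includes "Survival from fetal diagnosis to live birth". The confirmatory sequence in SAP 4.1 words the same item more narrowly, as live birth at 37 weeks or later.

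**The concern.** At the gestations at which fetuses enter this study, a fetus in difficulty after a procedure may be delivered alive and then die. Once born, that child can no longer be a fetal death, so both mortality rows pass it by.

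The procedure-linked death count then reflects centre practice as well as harm. Two centres could have the same complication and the same eventual death. The centre where the fetus dies in utero records an intervention-related death, and the centre that delivers does not. The study's stated aims include reducing variability between centres, and the Protocol says the results may support FAV programmes or lead to their being reconsidered.

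The Protocol (Publication of results) also allows procedural safety to be published before the 2-year outcome. That first paper would cover survival to neonatal discharge, but from all causes. Its procedure-linked death figure would still omit these cases.

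**Working it through.** **Step 1. Follow two cases with the same harm through the plan.** Both are FAV fetuses in the main analysis set. Case A dies in utero within 24 hours of the procedure. Case B is delivered alive within 24 hours and dies before neonatal discharge.

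| Where | Case A | Case B |
|---|---|---|
| Intervention-related fetal death (SAP 1.1, 3.5.3) | counted | not counted |
| Other fetal death (SAP 1.1, 3.5.3) | not counted | not counted |
| Reasons for death (SAP 3.5.3, Table 3.2.1) | listed | listed, with no link to the procedure |
| Primary composite (SAP 3.4.1) | failure | failure |
| Transplantation-free survival to 2 years (SAP 3.4.2) | event | event |
| Biventricular at discharge and at 2 years (SAP 3.4.2) | no | no |
| Survival to live birth (SAP 3.4.2) | death | survivor |
| Live birth at term (SAP 4.1, third test) | not a success | not a success |

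The last row assumes a procedure close to the inclusion window (up to 31+6 weeks), so that delivery within 24 hours is well before 37 weeks. Case B would also be counted under preterm delivery, together with preterm deliveries from any other cause.

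The cases differ in two mortality or survival measures: the first safety row, and survival to live birth as worded in SAP 3.4.2. High-risk fetuses (SAP 2.1.5) are outside the main analysis set. For them the efficacy rows apply only in the separate descriptive analysis, although they remain in the safety population.

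**Step 2. Size per event.** The documents state no procedural death rate, so there is no figure of the plan's to reproduce. Let n be the number of FAV fetuses, f the fetal deaths within 24 hours, and k the newborn deaths after delivery within 24 hours.

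- Rate from the existing row: f/n
- Rate with these newborn deaths shown: (f + k)/n
- Difference: k/n

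The planned n is 100 (SAP 1.5), so each death is 1/100 = 1.0 percentage point. The study may instead stop at 5 years. At the lower projected accrual of 10 FAV cases a year, n = 5 × 10 = 50, and each death is 1/50 = 2.0 points.

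**Step 3. Illustrations at n = 100.** Both f and k are assumed. Intervals are exact (Clopper-Pearson) 95% intervals.

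| f | k | Existing row | Combined (95% CI) |
|---|---|---|---|
| 5 | 0 | 5.0% | 5.0% (1.6 to 11.3) |
| 5 | 2 | 5.0% | 7.0% (2.9 to 13.9) |
| 5 | 5 | 5.0% | 10.0% (4.9 to 17.6) |
| 0 | 2 | 0.0% | 2.0% (0.2 to 7.0) |

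**Step 4. Chance that the issue arises at all.** With true risk q per fetus, the chance of at least one such death is 1 − (1 − q)^n. For example, 1 − 0.99^100 = 63%. The values of q are assumed.

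| q | n = 100 | n = 50 |
|---|---|---|
| 0.5% | 39% | 22% |
| 1% | 63% | 39% |
| 2% | 87% | 64% |
| 3% | 95% | 78% |

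Alpha, power and the primary analysis do not depend on any of this.

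**The case against.** The strongest reply is that nothing is mislabelled. The row is titled fetal death, it counts fetal deaths, and the documents never present it as total procedural mortality. Postnatal death is already named among the variables by which SAP 3.5.3 evaluates the procedure, and complications and deaths alike are only described. That is right, and it limits the point to a missing link between a postnatal death and the procedure.

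A reader might infer that the death all but disappears from the study. It does not: it counts against FAV in the primary composite, in transplantation-free survival and in both biventricular proportions when the case is in the analysis set.

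A reader might also infer that a centre that delivers gains on survival to live birth. That holds for the wording in SAP 3.4.2. It fails for the confirmatory version in SAP 4.1, under which a very preterm birth is not a success.

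Nor does the recorded item "Fetal resuscitation drugs used" show that such collapses are expected. It is one field in a list of technical details.

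Finally, a rule that calls every neonatal death after early delivery intervention-related would have its own bias. It would take in deaths from prematurity or the heart defect, and miss procedure-triggered deliveries after 24 hours. This objection stands. It is the reason for a separate row labelled by timing, with the existing definition left alone.

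**Conclusion.** The gap is real and follows from the wording alone: no safety row links a death after live birth to the procedure. Its consequence is conditional. Each newborn death after delivery within 24 hours of a procedure leaves the procedure-linked count 1 percentage point lower per 100 FAV fetuses than a combined count would be. If there are no such deaths, nothing changes.

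A stronger reading, that the plan understates procedural mortality by a known proportion, is not supported. Assuming 5 to 10 fetal deaths and 1 to 3 newborn deaths, the shortfall would run from 1/11 = 9% to 3/8 = 38% of the combined count. Both inputs are guesses, the newborn range leaves out zero, and the upper figure pairs the fewest fetal deaths with the most newborn deaths.

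This is an inexpensive improvement to safety reporting. It does not threaten the primary conclusion.

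**What to change.** Leave the row for fetal death within 24 hours unchanged. In SAP 3.5.3 and Table 3.2.1, and in the Protocol's Secondary objective so that the documents agree, add for FAV fetuses:

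- Delivery within 24 hours of a fetal procedure, with the number of live-born infants who then died in the neonatal period and the reason for each death. The SAP should state the day limit it uses for the neonatal period.
- The combined count of fetal deaths within 24 hours plus these neonatal deaths. Express it per fetus and not per procedure, because the eCRFs allow repeat interventions. Label it as temporally associated with the procedure and not as proven to be caused by it.

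Where survival to live birth is reported as worded in SAP 3.4.2, a footnote giving the number of these infants would be enough.

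The cost is one additional table row with its combined count, and short wording changes. The window will include some deaths due to prematurity or the underlying heart disease, and the procedural figure may look less favourable. The Protocol lists eCRFs for fetal interventions, birth and subject termination, but its summary does not show whether procedure and delivery times are recorded. The sponsor should confirm that the recorded dates and times support a 24-hour window before adopting the row.

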1.2 Study Design

The study is an international multicenter prospective observational cohort study with a comparison cohort. Included are fetuses with a diagnosis of aortic stenosis who satisfy inclusion/exclusion criteria between 23+0 and 31+6 weeks of gestation. The decision whether a fetal balloon dilatation shall be attempted is not part of the study protocol. The number of examinations of mother/fetus/infant in this study is not different from the number of examinations that will be recommended for someone choosing not to be part of this study. The participation in the study is not affecting the treatment mothers and fetuses are receiving during pregnancy, nor how the infant is examined and treated after birth. The aim of the study is to, in a prospective and organized way, collect and evaluate multi-center data in order to reduce the risk for selection bias, missing data and inter-variability between participating centers.

Cases will be recruited from centers offering fetal aortic valvuloplasty and and from centers not offering this treatment. All intervention cases will be recruited from high volume

Protocol

Statistical Analysis Plan

Effect of fetal aortic valvuloplasty on outcomes

1.0

intervention centres which have performed at least 20 fetal cardiac interventions during the last five years before including the first case in the study. Fetal and postnatal echocardiographic examinations will be reviewed and remeasured by a core laboratory to confirm eligibility for inclusion, and identify potential measurement errors.

Data from two fetal echoes and one postnatal will be collected and each contains a comprehensive set of two-dimensional and Doppler measurements which will enable analysis of cardiac growth and development during pregnancy. Analysis of change of dimensions of the left heart structures and selected hemodynamic variables from the point of study inclusion until just before the first postnatal catheter or surgical procedure provides an opportunity to make a comparison between the groups that is unbiased with respect to centerspecific postnatal treatment policies. Three echocardiographic examinations and a 2-year follow-up regarding patient outcome will be performed as per Figures 1-3 below.

Figure 1. Study Overview – Fetal Protocol

STATISTISKA KONSULTGRUPPEN	Statistic	cal Analysis Plan
Effect of fetal aortic valvuloplasty on outcomes	Protocol No:	
	Version: 1.0	Page 8 of 26

Figure 2. Study Overview – Neonatal Protocol

Figure 3. Study Overview – Protocol at Follow-up at 2 Years of Age

Protocols at Follow-up at 2 years of age				
24	months	36 months		
	Follow-up at 2 years	of age		
	eCRF 2 years follow	v-up		
eCRF Pos	tnatal procedure(s) eCRF	Subject termination		

1.3 Inclusion and Exclusion Criteria

1.3.1 Inclusion Criteria

Inclusion criteria represent currently used criteria for fetal intervention in aortic stenosis. They are identical in the intervention and the non-intervention groups.

Protocol

Statistical Analysis Plan

Effect of fetal aortic valvuloplasty on outcomes

Protocol No:

1.0

A. All of the following echocardiographic criteria need to be satisfied between 23+0 and 31+6 weeks (z-scores* according to schneider):

- 1 Aortic valve stenosis with antegrade flow through the valve
- 2 Predominantly left-to-right shunt at the atrial level
- 3 Predominantly retrograde flow in the aortic arch between the first two brachiocephalic vessels
- 4 Qualitatively depressed left ventricular function
- 5 LV end-diastolic diameter z-score* > +/-0
- 6 Left ventricular inlet length in diastole, z-score* according to gestational age
 - a. GA ≤ 24+6: Z-score > ±0
 - b. GA 25+0 to 27+6: Z-score > -0.75
 - c. $GA \ge 28+0$: Z-score > -1.50
- 7 Mitral valve diameter in diastole z-score* > -2.0
- B. All of the following postnatal treatment options need to be available:
- 1 Surgical or catheter based aortic valvotomy
- 2 Ross-Konno surgery
- 3 Norwood or hybrid stage-one surgery

1.3.2 Exclusion criteria

- 1. Any associated cardiac defect except persistent left superior vena cava and coarctation of the aorta.
- 2. Any significant (i.e. that might influence outcome) extracardiac anomaly and/or known chromosomal aberration. Also, if such a condition is present at inclusion but diagnosed only after birth the case will be retrospectively excluded.

1.4 Study Groups

The main analysis comparing intervention versus non-intervention will be on an intention-totreat, i.e. intention to perform fetal aortic valvuloplasty, basis. Intention to perform fetal valvuloplasty is defined as being present if the needle has been introduced through the maternal abdominal wall even if the fetal thorax has not been touched. Subjects will be Protocol

Statistical Analysis Plan

1.0

identified as belonging to the fetal aortic valvuloplasty (FAV) or the no-FAV groups as listed below.

The following groups will be identified:

- Subjects that undergo a technically successful fetal aortic valvuloplasty at a high volume intervention centre (FAV 1).
- Subjects with intention-to-treat (according to the above definition) at a high volume intervention centre but with no technical success (FAV 2).
- Subjects counselled at a center not performing or referring for fetal aortic valvuloplasty (no-FAV 1).
- Subjects counselled at a high- or low-volume intervention center, or at a center offering referrals to a center performing interventions, and the parental decision is to not perform fetal aortic valvuloplasty (no-FAV 2).

The main analyses will be to compare FAV 1+2 versus no-FAV 1+2. The expected proportion of enrolled fetuses/infants will be 2 [FAV] : 1 [no-FAV]. Complementary analyses will be comparing FAV 1 versus no-FAV 1, and FAV 1 versus no-FAV 1+2.

Figure 4. Main and complementary analysis

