## Electronic case report forms (eCRF)

There are 14 eCRF's:

1. eCRF Inclusion criteria

All inclusion and no exclusion criteria need to be satisfied for a case to be included.

2. eCRF Inclusion

Include case if inclusin/exclusion criteria satisfied.

3. eCRF Counselling on fetal aortic valvuloplasty

If councelling was performed and, if so, what the decision was.

4. eCRF Baseline fetal echo 23+0 - 31+6

The baseline fetal echo is performed between 23+0 and 31+6 weeks. If an intervention is performed, the last exam before the intervention should be used as baseline fetal echo.

5. eCRF Additional baseline fetal echo 23+0 - 31+6

In case there is a late descision to perform an intervention, after a baseline fetal echo has already been submitted, there is an option to add an additional baseline fetal echo in the system.

6. eCRF Fetal interventions

A new eCRF Fetal interventions should be added for each intervention performed.

7. eCRF Follow-up fetal echo 33+0 - 34+6

The follow-up fetal echo is performed between 33+0 and 34+6 weeks.

8. eCRF Neonatal - Birth

Gestational age and size at birth, mode of delivery and pharmacological support.

9. eCRF Neonatal - Echo

First full study after birth, and before the first postnatal intervention, surgery or cath (except emergency atrial septostomy)

10. eCRF Neonatal - Cardiac clinical diagnosis

Cardiac diagnoses before the first intervention, surgery or cath (except emergency atrial septostomy)

11. eCRF Neonatal - Neonatal discharge

Type of circulation and clinical diagnoses at discharge.

12. eCRF Follow-up at 2 years of age

Type of circulation, clinical diagnoses, pulmonary hypertension, neurological sequealae, somatic growth.

13. eCRF Postnatal procedures

All cardiac surgical and catheter interventional procedures from birth to 2 years follow-up

14. eCRF Subject termination

Reason for subject termination including completion at 2 years of age.

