Cases with termination of pregnancy after study inclusion will be excluded from analysis but numbers noted.

Subgroup analyses will be performed for:

- Subjects with diagnosis of fetal aortic stenosis that undergo technically successful fetal aortic valvuloplasty and additional fetal cardiac intervention(s) such as atrial septal balloon dilatation or stent placement.
- b. Subjects with diagnosis of fetal aortic stenosis and hydrops.
- c. Subjects with diagnosis of fetal aortic stenosis, severe mitral regurgitation and left atrial enlargement with or without restrictive or intact atrial communication and with or without hydrops.

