2 STUDY POPULATIONS

2.1 Definition of Study Populations

2.1.1 Full Analysis Set for All Enrolled

Fetuses with severe MR and severe LA enlargement and/or intact or highly restrictive interatrial communication and/or cases with hydrops present at inclusion are all high-risk cases regarding survival, but may have a rather good prognosis if they survive the first critical period. It is likely they will be overrepresented in the FAV group to such a degree that it will be difficult to control for through propensity score matching. Therefore this subpopulation will be excluded from the full analysis set and analysed separately. Fetuses developing any of these conditions after inclusion will not be excluded from the full analysis set.

All enrolled fetuses that have satisfied inclusion/exclusion criteria and belong to FAV 1+2 and no-FAV 1+2 groups and not listed as belonging to the high-risk population described above will be included in the Full Analysis Set enrolled (FAS_{ENR}) population. Infants wrongly included in the study (not fulfilling all inclusion or fulfilling any of the exclusion criteria) will not be part of the FAS_{ENR} population, but will be described in the safety analyses. As detailed under 1.3.2, also subjects with exclusion criteria present at inclusion but diagnosed only after birth will be retrospectively excluded from the FAS_{ENR} population.

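### The main comparison is labelled intention-to-treat but assigns FAV only at needle entry, so a fetus whose parents chose FAV and who never reached the needle is in no group and drops out of the primary analysis

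*SAP*

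**What the plan says.** SAP 1.4 Study Groups, and the same text in the protocol under Data analysis and statistical support, set the main analysis on an intention-to-treat basis and then define intention: "Intention to perform fetal valvuloplasty is defined as being present if the needle has been introduced through the maternal abdominal wall". The four groups are:

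- FAV 1: "Subjects that undergo a technically successful fetal aortic valvuloplasty at a high volume intervention centre (FAV 1").
- FAV 2: "Subjects with intention-to-treat (according to the above definition) at a high volume intervention centre but with no technical success (FAV 2").
- no-FAV 1: counselled at a centre that neither performs FAV nor refers for it.
- no-FAV 2: counselled where FAV is performed or referral is offered, "and the parental decision is to not perform fetal aortic valvuloplasty (no-FAV 2").

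SAP 2.1.1 restricts FAS_ENR to eligible enrolled fetuses that "belong to FAV 1+2 and no-FAV 1+2 groups and not listed as belonging to the high-risk population". SAP 4.6.1 runs the confirmatory primary test on FAS_ENR, FAV 1+2 against no-FAV 1+2. The safety population (SAP 2.1.6) holds all enrolled fetuses, but its complications and reasons for death are described without formal tests (SAP 4.7.3).

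The protocol's list of eCRFs has a counselling form that records: "If councelling was performed and, if so, what the decision was". It also provides an additional baseline echo form for a late decision to intervene. SAP 3.1 collects maternal contraindications to fetal intervention.

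The first secondary variable in SAP 3.4.2 is "Transplantation-free survival from fetal diagnosis to 2 years of age (analysed as time to event"), so its clock starts at diagnosis. On terminations the protocol says: "Cases with termination of pregnancy after study inclusion will be excluded from analysis but numbers noted".

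**The concern.** Under intention to treat, an early failure stays in the arm that was chosen. Here the FAV arm begins when the procedure begins. A fetus with a decision for FAV that dies in utero while waiting has not had the needle, was not counselled at a centre without access to FAV, and has no parental decision against it. It belongs to no group, so FAS_ENR excludes it. A fetus in the comparison group that dies over the same weeks is kept as a failure. Not being attempted because of a maternal contraindication leads to the same gap.

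Adjustment for confounders known at inclusion cannot bring back deleted cases, and neither can propensity matching within the same analysis sets. The protocol's closing section says the result may support FAV programmes or cause them to be reconsidered, so the contrast should be the one its label promises.

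The survival outcomes have a related time-zero problem. Every fetus must survive from diagnosis to inclusion, and a FAV fetus must also survive to the needle.

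**Working it through.** **Step 1. Classify the case.** Take an eligible, enrolled fetus, not high-risk, with a decision for FAV at a high-volume centre and no needle entry.

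| Group | Condition | Met? |
|---|---|---|
| FAV 1 | procedure done, technically successful | no |
| FAV 2 | needle entered, no technical success | no |
| no-FAV 1 | counselled where FAV is neither performed nor referred for | no |
| no-FAV 2 | parents decided against FAV | no |

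No group applies, so the fetus is not in FAS_ENR. No readable text assigns it elsewhere in the efficacy analyses. The late-decision form shows that a gap between enrolment and procedure is foreseen.

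**Step 2. Reproduce the plan's power.** Inputs from SAP 1.5: 100 versus 50, 60% versus 30%, two-sided Fisher's exact test, alpha 0.05. Enumerating both binomials gives 92.7% (stated 91.8%). For 100 versus 100 it gives 98.9% (stated 98.7%). These figures are close enough and are not in dispute. The exact size at 30% versus 30%, 100 versus 50, is 4.0%.

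**Step 3. Effect of dropping the lost fetuses when FAV does nothing.** Let f be the share of FAV-decided fetuses that never reach the needle and s their success rate. Both are assumptions, because the documents give neither. With 30% success in both arms by decision:

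apparent FAV rate = (0.30 − f·s) / (1 − f)

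Example: f = 0.10, s = 0 gives 0.30 / 0.90 = 33.3%. The odds ratio is (0.333/0.667) / (0.30/0.70) = 1.17. Because recruitment aims at 100 FAV cases, rejection is computed at 100 versus 50.

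| f | s | Apparent FAV rate | Odds ratio | Fisher rejection |
|---|---|---|---|---|
| 5% | 10% | 31.1% | 1.05 | 4.2% |
| 5% | 0% | 31.6% | 1.08 | 4.4% |
| 10% | 10% | 32.2% | 1.11 | 4.7% |
| 10% | 0% | 33.3% | 1.17 | 5.7% |
| 20% | 10% | 35.0% | 1.26 | 7.9% |
| 20% | 0% | 37.5% | 1.40 | 13.0% |

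If s = 30% the formula returns 30% for every f, so there is no bias. If s = 40% and f = 20% it gives (0.30 − 0.08)/0.80 = 27.5%, and the bias runs against FAV.

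**Step 4. If such cases were read into no-FAV 2.** This could happen if parents formally decide against FAV once the fetus deteriorates. With planning rates (60 of 100, 15 of 50) and 11 such cases, none successful, the no-FAV rate becomes 15/61 = 24.6%. The difference rises from 30 to 35.4 points, again in favour of FAV. A death before the needle after a decision for FAV cannot be read this way.

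**Step 5. Time zero.** Diagnosis to inclusion is guaranteed survival in both groups. Inclusion to needle is guaranteed only in FAV. The outcomes affected are the time-to-event ones, which stand second and third in the testing sequence of SAP 4.1.

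**The case against.** The strongest reply is that the needle rule is openly stated and the effect may be negligible. In FAV cases the baseline echo is the last one before the procedure, and a late decision is handled as an exception, which suggests a short gap. At 5-10% lost the rejection rate barely moves. The calculation is also an unadjusted Fisher test, whereas the primary analysis is adjusted logistic regression. All of this stands as a limit on size. It does not fill the gap in the group definitions, and a short wait is suggested but not shown.

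A reader might infer that every bad outcome is removed from the FAV arm alone. The documents do not support that. A maternal contraindication need not predict fetal outcome, and a fetus that became unsuitable because it improved would shift the result the other way. Only for deaths is the direction certain.

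A reader might infer that all time from diagnosis is immortal for FAV only. Survival to inclusion is required in both groups under identical criteria, so only the inclusion-to-needle interval is inherently differential.

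A reader might also infer that protocol and SAP use different denominators, because the SAP 2.1.1 text does not list terminations among its exclusions. The legends of SAP Figures 5 and 6 define ToP, and those figures are not shown in the text available here. SAP section 6 reports no significant change from the protocol. A contradiction cannot be asserted.

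**Conclusion.** The point holds on the wording of SAP 1.4, 2.1.1 and 4.6.1: the main contrast is by procedure started, under an intention-to-treat label, and its denominator omits FAV-decided fetuses that never reached the needle. Deaths omitted in this way bias the primary result towards FAV. For other omissions the direction follows the prognosis of those lost.

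The size cannot be learned from the documents. It is small if about 5% are lost and material only towards 20% with poor outcomes. A claim that the false-positive rate is seriously inflated would rest on that upper assumption and is not supported. What is established is that the primary analysis, as defined, does not include these fetuses and would not show the effect of their loss. Figures 4 to 6 of the SAP were not available and could depict them; if so, the text still needs to agree.

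**What to change.** 1. In SAP 1.4 and 2.1.1, and the matching protocol text, assign eligible enrolled fetuses to an arm by a specified decision on the counselling eCRF, for example the last one recorded before any needle entry or death. Count a decision for FAV at a high-volume centre as FAV whether or not the needle entered. This keeps the high-volume restriction. State how to class a fetus with no counselling or no decision recorded, and report changes of decision, since a switch after deterioration would move a poor prognosis into the comparator.
2. Keep the needle-based FAV 1+2 contrast as a complementary analysis.
3. At minimum, report the number and outcomes of ungrouped fetuses, and pre-specify a sensitivity analysis of the primary endpoint that counts them as FAV.
4. For the time-to-event outcomes (SAP 3.4.2 and 4.1), start follow-up at inclusion or use delayed entry there. Grouping by decision then removes the FAV-only guaranteed time between decision and needle.
5. Check the SAP text against the protocol's exclusion of terminations and state the rule in words as well as in Figures 5 and 6.

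**Cost.** This is a change of wording; the decision is already collected. The FAV effect is diluted by unattempted cases. If the planned 60% applies to 100 needle-entered fetuses, f of 5, 10 or 20% adds 100·f/(1 − f), about 5, 11 or 25 fetuses. With s from 0 to 30%, the FAV rate, (60 + k·s)/(100 + k) for k added fetuses, becomes 57.1-58.6%, 54.1-57.0% or 48.0-54.0%. Power becomes 87.6-90.9%, 79.6-88.3% or 57.4-82.4%, against 92.7%. The dilution is slight if few are lost. If many are lost, it measures what the needle-based contrast leaves out.
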